Enhanced Diagnostic Workup for Patients About to Start Empiric Tuberculosis Treatment in Lusaka, Zambia

NCT-number: not yet assigned

Version: 8-12-2024

Background and justification: Tuberculosis remains a common disease worldwide, with an estimated 10 million new cases in 2020. It is one of the leading causes of death worldwide, causing an estimated 1,3 million deaths in 2020.¹ In Sub-Saharan Africa in particular, the combined burden of tuberculosis and human immunodeficiency virus (HIV) infection leads to increased tuberculosis prevalence and mortality. Tuberculosis is a treatable disease, and most, if not all, deaths could be prevented by timely diagnosis and appropriate treatment. Unfortunately, diagnosing tuberculosis can be challenging.² Several diagnostic strategies have been developed, but the most impactful development in recent years has been the widespread implementation of the GeneXpert MTB/RIF test. This is a cartridge-based nucleic acid amplification test, which can be used with minimal supporting laboratory structure, and has an estimated sensitivity and specificity for diagnosing pulmonary tuberculosis in adults of 85% and 98%, respectively.^{1,3}

The GeneXpert MTB/RIF test replaced sputum smears for acid-fast bacilli as a first-line test, which had much lower sensitivity for diagnosing pulmonary tuberculosis. Historically, this lower sensitivity meant that clinicians also had to rely on clinical factors to determine whether to start tuberculosis treatment. Currently, the practice of giving empiric tuberculosis treatment to patients who had negative microbiology diagnostics is still widespread.⁴⁻⁷ However, in the GeneXpert MTB/RIF era, this might no longer be appropriate.⁸⁻¹¹

For example, in Zambia, there were an estimated 40000 new tuberculosis cases in 2020 (with 92% pulmonary tuberculosis), 100% of whom were tested with GeneXpert MTB/RIF (or other rapid molecular diagnostics). However, only 51% of all patients who were treated for pulmonary tuberculosis were bacteriologically confirmed.¹ This is not consistent with the supposed 85% sensitivity of the GeneXpert MTB/RIF test. This might mean that a significant proportion of patients, perhaps in the order of 30-40% of all patients, and 60-80% of all empirically treated patients, receives tuberculosis treatment inappropriately. Standard tuberculosis treatment can be burdensome, as the usual treatment duration is 6 months, and 5-10% of patients are estimated to experience serious side effects.² In some cases, a self-limiting condition such as a viral respiratory tract infection might be the underlying diagnosis, which would not need to be followed up for six months. More importantly, empiric tuberculosis treatment can delay the diagnosis of another severe underlying condition such as malignancy, pulmonary aspergillosis, or interstitial lung disease. It has been shown that mortality is higher in patients that are empirically treated for tuberculosis, and this may be in part to missed other diagnoses.¹²

Over the past years, the departments of pulmonology and radiology from St. Antonius Hospital have been holding bimonthly videoconferences with the department of pulmonology at University

Teaching Hospital in Lusaka, Zambia. We have mainly discussed patients with suspected interstitial lung disease. Our experience has taught us that interstitial lung diseases, which have barely been reported in Sub-Saharan Africa, can indeed be identified when you look well enough, and that these patients have oftentimes received inappropriate empiric tuberculosis treatment prior to the diagnosis of interstitial lung disease.^{26,27}

In recent years, specialty services, such as a pulmonology clinic, as well as computed tomography (CT)-scanning and novel microbiological tests have become available in Zambia, as well as other developing countries. This, in combination with the widespread availability of the high-sensitivity GeneXpert MTB/RIF test, leads us to believe that common practice of giving empiric tuberculosis treatment after a negative initial microbiological test for tuberculosis is no longer appropriate. In this study we want to explore the feasibility of an enhanced diagnostic workup for patients about to start empiric tuberculosis treatment and the impact this has on patient diagnoses and outcomes. This workup will include discussing patients in international multidisciplinary videoconferences when needed.

Societal relevance: No specific societal relevance.

Economic relevance: Might be associated with cost savings if tuberculosis treatment can be avoided, if long follow-up is avoided for self-limiting conditions and if severe conditions are diagnosed and treated in a timelier manner.

Medical relevance: Appropriate diagnosis and treatment are the cornerstone of medicine. This is in accordance with the principles of beneficence and non-maleficence. If the enhanced diagnostic workup does indeed lead to more appropriate diagnosis and treatment, this likely impacts patient quality of life and might even impact patient survival.

Other relevance: If the study findings are positive, this will justify the further building of specialty services as an addition to program-based tuberculosis services in Zambia and other developing countries.

Statement of the problem:

Tuberculosis is often diagnosed on a clinical basis, even with the widespread availability of highly sensitive laboratory tests such as GeneXpert MTB/RIF. This might lead to overtreatment of tuberculosis, as well as misdiagnosis and incorrect or delayed treatment for other respiratory diseases.

Literature review: A recent systematic review found that over half of patients with presumed tuberculosis (i.e. patients in whom tuberculosis was considered as a diagnosis, but who did not necessarily receive empiric tuberculosis treatment) do not have a final diagnosis of active tuberculosis, but little is known about the healthcare needs of these patients.¹³ A study from the United Kingdom found that the rate of misdiagnosis was 10.8%, and was higher in patients with pulmonary tuberculosis who had a negative sputum smear.¹⁴ In a study from the Republic of Korea, the rate of misdiagnosis of TB was not reported in clinically diagnosed patients, but the main alternative diagnoses in patients that were misdiagnosed as pulmonary TB were infections with non-tuberculous mycobacteria, bacterial pneumonia, and malignancy.¹⁵

There are several previous studies into alternative diagnoses in patients who were empirically treated for tuberculosis, but high-quality evidence is lacking. The only prospective study was done in Tanzania, and included 36 patients. Of these patients, 23 completed all additional investigations, and only 2 of these patients (6%) were confirmed to have tuberculosis. The other patients were diagnosed with pneumonia, bronchiectasis, interstitial lung disease, non-tuberculous pleural disease, malignancy, and chronic pulmonary aspergillosis.¹⁶ A retrospective study in Pakistan found that 45% of 61 patients who received empiric treatment later were found to have an alternative diagnosis, including malignancies, heart failure, chronic pulmonary aspergillosis, and bronchiectasis.¹⁷ In another study by the same authors, it was found that over a third of patients with allergic bronchopulmonary aspergillosis in a Pakistani tertiary care hospital, had initially been misdiagnosed as tuberculosis.¹⁸ In a study from Nigeria, it was found that a significant proportion of patients that were re-treated for tuberculosis, and had been classified as treatment failures, actually had chronic pulmonary aspergillosis.¹⁹ What complicates matters, is that pulmonary aspergillosis is frequently seen as a late complication of cavitary tuberculosis, even if the latter has been adequately treated.²⁰ A recent systematic review highlighted 80 cases in which various types of pulmonary fungal infections were initially misdiagnosed as tuberculosis.²¹ Furthermore, a study from South-Africa found that almost all patients who were treated for lymphoma at a tertiary level hospital, had received empiric tuberculosis treatment in the year prior.²² A study from Uganda found a lower, but still significant rate of 30% misdiagnosis of tuberculosis in patients with HIV-associated lymphoma.²³ A study from Malawi in a general oncology department found a misdiagnosis as tuberculosis in 1% of all referred patients.²⁴

Interestingly, in another study from Uganda, it was found that 88% of 162 patients who received a course of broad-spectrum antibiotics instead of empiric tuberculosis treatment, showed clinical improvement and 4% were treated for an alternative respiratory disease.²⁵

Type of research: prospective intervention study

Research question: does an enhanced diagnostic workup for patients about to start empiric tuberculosis treatment in Lusaka, Zambia, lead to alternative diagnoses and improved patient outcomes after six months?

Primary objective: to determine in what proportion of patients who are about to start empiric tuberculosis treatment, an alternative diagnosis can be made through the use of a concise additional workup by an experienced pulmonary physician, including review of available data, as well as additional laboratory, functional, and imaging investigations

Secondary objectives: to determine whether establishing and treating alternative diagnoses in patients who were about to start empiric tuberculosis treatment leads to improved quality of life and survival after six months

In- and exclusion criteria: All adult patients who have a negative initial GeneXpert MTB/RIF test on sputum, but are about to start standard first-line treatment for suspected pulmonary tuberculosis on clinical grounds (i.e. empiric tuberculosis treatment), at four first-level Hospitals in Lusaka, Zambia. Patients will be excluded if they are inpatients (due to suspected tuberculosis).

Number of eligible patients per year: Estimated 410 eligible patients per year in Chawama (450 clinically diagnosed pulmonary tuberculosis patients at Chawama first-level hospital in 2023, including children). The total population at Chawama first-level hospital in 2023 included 5361 presumptive tuberculosis cases, of whom 5270 had GeneXpert MTB/RIF testing done, and of whom 426 had a positive result from GeneXpert MTB/RIF. There is a discrepancy with the number of bacteriologically confirmed tuberculosis cases, which is reported at 663 for the year. The reason for this is not entirely clear, but might be due to additional testing being performed at different facilities, and the use of other tests for diagnosing tuberculosis, such as lipoarabinomannan assay and acid-fast bacilli smear. Interestingly, the percentage of patients who had a tuberculosis relapse was higher in patients being treated empirically than in patients with bacteriologically confirmed tuberculosis (107 out of 450 (24%) versus 107 out of 663 (16%)).

Treatment outcomes for 2022 are as follows: 618 bacteriologically confirmed new cases of which 523 were cured (85%), 29 completed treatment, 36 died (6%), 3 failed treatment, 24 were lost to follow up, and 3 were not evaluated; 123 bacteriologically confirmed tuberculosis relapses of which 115 were

cured (93%), 5 died (4%), 2 were lost to follow up, and 1 was not evaluated; 352 clinically diagnosed new cases of which 308 completed treatment (88%), 35 died (10%), 1 failed treatment, 7 were lost to follow up, and 1 was not evaluated; 156 clinically diagnosed tuberculosis relapses of which 143 completed treatment (92%), 9 died (6%), and 3 were lost to follow up.

The other first-level hospitals had somewhat lower numbers of patients in 2023.

Intervention: All included patients will undergo the study intervention. Participants will be included from the tuberculosis clinic at first-level hospitals. They will be reviewed by one of the study physicians prior to initiating empiric tuberculosis treatment. A full history and physical examination will be taken and available results will be reviewed (laboratory results, sputum results, and chest X-ray). Depending on the results, appropriate measures will be taken there, including possible treatment with antibiotics or a wait-and-see approach for suspected viral infections. If further diagnostics are deemed to be indicated, a patient will be referred to the pulmonology clinic at University Teaching Hospital in Lusaka, Zambia. There, appropriate additional diagnostics will be requested, including additional blood tests (such as aspergillus serology), repeat chest X-ray, spirometry, CT-scan of the chest (if no other clear clinical diagnosis), bronchoscopy (if indicated based on CT-scan) and sputum and/or bronchial washing bacterial and mycobacterial cultures. The empiric treatment will be withheld initially if the study investigator thinks that an alternative diagnosis is more likely, while awaiting the additional investigations. If the study investigator thinks it is in the interest of the patient, then empiric tuberculosis treatment will be initiated while awaiting the results for the additional investigations. When a final diagnosis is made, appropriate treatment decisions will be made. If a clear diagnosis cannot be made locally, patients will be discussed in a multidisciplinary team meeting between St. Antonius Hospital and University Teaching Hospital.

Methods: Participants will be asked to participate in the study once the clinician at the first-level hospital has decided to start empiric tuberculosis treatment. If the patients provide written informed consent, they will be reviewed by the study physician on-site, and possibly referred for further investigations as described above. Quality of life will be assessed at baseline, as well as during follow up. Patients will be followed up for 6 months, at which time every patient file will be reviewed by a study investigator and the final diagnosis will be determined.

Primary outcome: diagnosis at 6 months (tuberculosis versus alternative diagnosis)

Secondary outcomes: quality of life at 6 months (EUROHIS-QOL), change in quality of life from baseline to 6 months (EUROHIS-QOL), survival at 6 months, number of patients that received tuberculosis treatment, number of patients that had side effects attributed to tuberculosis treatment,

Number of patients to include: 300

Sample size calculation: The power is set at 80% and α at 0.05. Assuming a 10% mortality in the historic control group (based on 2022 tuberculosis outcome data from Chawama first-level hospital), and a 5% mortality in the intervention group, 238 patients will have to be included. A safety margin of 20% of refusal to participate in the study and loss to follow up is assumed, so that approximately 300 patients will have to be included.

Statistical analysis: Descriptive statistics will be used to describe percentage of alternative diagnoses, as well as percentage of patients that has quality of life scores indicating they are not satisfied or very dissatisfied, the percentage of patients who received tuberculosis treatment and the percentage of patients that had side effects attributed to tuberculosis treatment. Paired analyses will be used to compare quality of life at baseline and during follow up. Multivariate regression analyses will be used to identify what factors associate with quality of life and survival. We will use per-protocol analysis methods for the primary analyses, with intention-to-treat analyses as a secondary tool. We will use a historic control group of patients who underwent empiric TB treatment at the study sites in the year prior to the study as a comparison for survival. Additionally, as data for the tuberculosis clinic are collected in a standard fashion, it will be able to compare the number of patients being referred to the clinic, the number of patients receiving treatment for bacteriologically confirmed tuberculosis, and the number of patients receiving empiric tuberculosis treatment, as well as treatment outcome data, between the study period and the period prior to and after the study.

Burden and risks for participants: The burden for the participants consists of having to travel to University Teaching Hospital (4.2 km – 10.6 km distance) for review and potential additional investigations that cannot be done on the same day (CT-scan and bronchoscopy). The additional investigations might necessitate venepuncture (slightly painful, low risk of hematoma or bleeding), chest X-ray (low dose radiation (0.1mSv)), spirometry (low risk of feeling uncomfortable), and

potentially CT-scan of the chest (medium dose radiation (6.1 mSv)), and bronchoscopy (discomfort for most patients, risk of serious complications (e.g. bleeding, pulmonary oedema, pneumothorax) ca. 1%). It needs to be emphasized that these investigations would be considered as the standard-of-care in a high-resource setting, and, in that sense, are not actually an additional burden at all.

Study duration: 16 months

Start date: 1/12/2024

Final inclusion: 31/12/2025

End date: 30/06/2026

Dissemination plan:

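### Culture, CT and bronchoscopy depend on discretionary referral, yet the primary outcome is one ungraded two-way label, so the headline percentage carries a bias of unknown size and sign

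*Combined protocol and SAP*

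**What the plan says.** Under Intervention, every participant has an on-site history, examination and review of existing results. Some are managed there, with "possible treatment with antibiotics or a wait-and-see approach for suspected viral infections" given as examples. For the rest, "If further diagnostics are deemed to be indicated, a patient will be referred to the pulmonology clinic at University Teaching Hospital". Methods repeats that participants are seen and then "they will be reviewed by the study physician on-site, and possibly referred for further investigations as described above". No referral criteria and no expected referral share are given.

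The tests that could separate tuberculosis from other disease are listed only at the referral clinic. They include "sputum and/or bronchial washing bacterial and mycobacterial cultures". Imaging and endoscopy are conditional even there: "CT-scan of the chest (if no other clear clinical diagnosis), bronchoscopy (if indicated based on CT-scan".

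The Primary outcome is "diagnosis at 6 months (tuberculosis versus alternative diagnosis". According to Methods, one study investigator reviews each file at six months and sets the final diagnosis. No diagnostic criteria, certainty grade or undetermined class appears. Statistical analysis plans a descriptive percentage of alternative diagnoses, without a breakdown by verification and without a sensitivity analysis.

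**The concern.** Whether a patient is cultured or scanned depends on the same clinical judgement that the outcome is meant to assess. A patient called a viral infection on site and a patient with a negative mycobacterial culture and a specific CT diagnosis both add one to the numerator. A tuberculosis label that was never cultured and one that was culture-confirmed both stay out of it. No sentence says that these labels count equally. It follows from a two-way outcome with no grading and a simple percentage.

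This is the primary endpoint, and under Other relevance positive findings are meant to support expanding specialty services. A reader of the single percentage could not tell how much of it rests on tests and how much on clinical impression.

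**Working it through.** **The plan's own figure.** The only sample size calculation concerns mortality, 10% against 5%. A two-sided one-sample test reproduces it: n = (1.960 × √(0.10 × 0.90) + 0.842 × √(0.05 × 0.95))² / 0.05² = 238.03. Then 238 / 0.80 = 297.5, or about 300. Neither figure was chosen for the primary proportion. They serve here only as the range of analysable patients.

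**Sampling error of the primary proportion.** Half-width = 1.96 × √(p(1 − p)/n).
- p = 0.5, n = 238: 6.4 points.
- p = 0.8, n = 300: 4.5 points.

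**Bias from unequal verification.** Let f be the share of patients not referred, a the share of those labelled alternative, e1 the share of those alternative labels that are in truth tuberculosis, and e2 the share of the non-referred tuberculosis labels that are in truth something else. Then

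bias = f × [a × e1 − (1 − a) × e2].

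The documents give none of these four quantities, so every value below is an assumption. The nearest anchor is Background and justification, which suggests that perhaps 60–80% of empirically treated patients do not have tuberculosis. That implies 20–40% who do.

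*Upward part alone*, writing s = f × a for the share labelled alternative without culture:

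| s | e1 | s × e1 |
|---|---|---|
| 30% | 10% | 3 points |
| 30% | 20% | 6 points |
| 60% | 10% | 6 points |
| 60% | 20% | 12 points |

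These values give no credit for what six months of follow-up may correct.

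*Both parts together:*

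| f | a | e1 | e2 | Bias |
|---|---|---|---|---|
| 50% | 100% | 20% | – | 0.50 × 0.20 = +10 points |
| 50% | 90% | 10% | 60% | 0.50 × (0.09 − 0.06) = +1.5 points |
| 50% | 70% | 10% | 60% | 0.50 × (0.07 − 0.18) = −5.5 points |
| 50% | 50% | 20% | 60% | 0.50 × (0.10 − 0.30) = −10 points |

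The two errors cancel at e2 = e1 × a/(1 − a). With a = 70% and e1 = 10% this is 0.10 × 0.70/0.30 = 23%. If more than 23% of the unreferred tuberculosis labels are wrong, the proportion is understated.

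**A lower anchor.** The Literature review cites a prospective Tanzanian study with 2 confirmed cases: 2/36 = 6% of all patients, or 2/23 = 8.7% of those fully investigated. Used as e1, these give 0.30 × 0.06 = 1.8 points to 0.60 × 0.087 = 5.2 points. The sample is small, and confirmed cases are a minimum for true cases.

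**The case against.** The strongest reply is that the label counted is the six-month diagnosis and not the on-site impression. Every file is reviewed, so a patient sent home with a presumed viral infection who worsens, or is later confirmed to have tuberculosis, can be reclassified. All participants also enter with a negative GeneXpert. The Primary objective asks what an experienced physician can diagnose, and it expressly includes reviewing existing data, so on-site diagnoses are meant to count. All of this stands. It means that patients who are not referred are less verified, not unverified, and that the planned percentage is a legitimate headline. It does not make verification equal: the plan does not say what course over six months supports either label, and recovery after treatment does not settle the diagnosis.

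Three stronger readings are tempting, and the documents support none of them.

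- *That the proportion is overstated.* The on-site measures named under Intervention do point towards alternative labels. But that list is given as examples, and uncultured tuberculosis labels are not ruled out. If they are often wrong, the bias is downward.
- *That patients in whom tuberculosis is doubted are tested least.* Intervention describes withholding empiric treatment when an alternative seems more likely, pending further investigations. Doubted patients are thus expressly among those investigated.
- *That the protocol itself predicts frequent concurrent disease.* The Literature review does say that "pulmonary aspergillosis is frequently seen as a late complication of cavitary tuberculosis", but the sentence goes on to say that this holds after adequate treatment as well. It describes a late sequel, which here could be a true alternative diagnosis. The relapse share at one hospital (107/450 = 24%, under Number of eligible patients per year) does not show dual disease either. What remains is that the two-way outcome has no stated rule for a patient who has both.

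**Conclusion.** The concern holds as one of differential verification without grading. Culture, CT and bronchoscopy are described only after a discretionary referral, and the primary percentage mixes test-supported and purely clinical labels. The net bias cannot be computed from the documents, and neither can its sign. On assumed inputs (30–60% labelled alternative without culture, 10–20% of those truly tuberculosis) the upward part alone is 3–12 points before credit for follow-up, or about 2–5 points with the Tanzanian figures. The 95% half-width is 4.5–6.4 points. The low end therefore lies within sampling error and the high end well beyond it. Assumed errors in uncultured tuberculosis labels can turn the net bias to −5.5 or −10 points. The case for acting does not depend on the direction, because the planned analysis gives a reader no means of judging it.

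**What to change.** Keep the planned percentage of alternative diagnoses as the headline. Making only the verified diagnoses the numerator would change the Primary objective. Add to Statistical analysis, before final diagnoses are tabulated, a table that grades **both** labels from data already collected:

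- (a) supported by a specific positive test or by a mycobacterial culture result, showing whether culture was done, since a positive test for another disease does not exclude tuberculosis;
- (b) clinical label supported by the six-month course. For an alternative diagnosis this means well at six months without tuberculosis treatment. The investigators should state the matching criterion for a tuberculosis label, given that recovery on treatment alone does not separate the two;
- (c) clinical label not so supported, or undetermined.

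Show any patient with both diseases on a separate line, counted as tuberculosis in the two-way outcome.

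Report the proportion by referral status and by verification level. Then give the range with all level (c) patients, whichever label they carry, counted once as tuberculosis and once as alternative. If A patients hold an alternative label at level (a) or (b), C are at level (c) and N are analysed, the range runs from A/N to (A + C)/N. Its width is the share at level (c).

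The cost is one paragraph, one table and a wider stated uncertainty around the headline. No test, visit or change in management is added.

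### The plan describes no review of deaths during enrolment and no rule for pausing it, although the single-arm intervention allows tuberculosis treatment to be withheld initially

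*Combined protocol and SAP*

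**What the plan says.** - **Design (Intervention):** "All included patients will undergo the study intervention". There is no concurrent comparison group.
- **Withholding (Intervention):** "The empiric treatment will be withheld initially if the study investigator thinks that an alternative diagnosis is more likely, while awaiting the additional investigations". The same section allows the opposite course where the investigator judges it to be in the patient's interest: "then empiric tuberculosis treatment will be initiated while awaiting the results for the additional investigations". Under Methods, patients are approached only after the site clinician has chosen to start empiric treatment.
- **Follow-up (Methods):** "Patients will be followed up for 6 months, at which time every patient file will be reviewed by a study investigator". The stated purpose of that review is to settle the final diagnosis. Quality of life is also assessed during follow-up, at times not given.
- **Mortality (Secondary outcomes, Sample size calculation, Statistical analysis):** survival at 6 months is a secondary outcome, compared with a historic group from the year before the study. The sample size rests on "Assuming a 10% mortality in the historic control group" and 5% under the intervention.
- **Risk (Burden and risks for participants):** the section opens with "The burden for the participants consists of having to travel to University Teaching Hospital" and goes on to blood sampling, radiation, spirometry and bronchoscopy. Delayed tuberculosis treatment is not mentioned.
- **Monitoring:** the documents contain no interim look at mortality, monitoring committee, death-reporting process or pause rule.

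**The concern.** Where treatment is withheld and the patient does have tuberculosis, the delay is caused by the study. The plan's own premise makes such patients likely to be present: Background and justification suggests, with hedging, that perhaps "60-80% of all empirically treated patients, receives tuberculosis treatment inappropriately", which leaves 20-40% treated appropriately. With one arm, an excess of deaths cannot show as a difference between concurrent groups. It can show only if someone counts deaths against a benchmark while patients are still being enrolled, and nobody is given that task. The plan already holds a benchmark, because it sizes the study on mortality. The point concerns acting on deaths during the study, not which harms are reported at the end.

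**Working it through.** **1. The plan's own figure.** A one-sample test against a fixed 10%, two-sided alpha 0.05, 80% power, alternative 5%:

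n = (1.96 × √(0.10 × 0.90) + 0.8416 × √(0.05 × 0.95))² / 0.05² = 238.03.

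This reproduces 238, and 238/0.8 = 298, or about 300. The plan therefore already treats 10% as a fixed reference.

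**2. Where the 10% comes from.** Among clinically diagnosed patients in the 2022 outcomes, 35/352 = 9.9% of new cases and 9/156 = 5.8% of relapses died. Pooled, 44/508 = 8.7%. Relapses are not excluded from the study, so 8.7% is a reasonable sensitivity value.

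**3. Enrolment before the first scheduled review.** Inclusion runs from 1/12/2024 to 31/12/2025, which is 396 days. The first patient reaches six months on 1/6/2025, after 182 days. With even accrual (my assumption), 300 × 182/396 = 138. Two alternatives:
- The stated duration of 16 months conflicts with the 19 months implied by the dates. It would leave 10 months for accrual: 300 × 6/10 = 180.
- One site enrolling all of its estimated 410 eligible patients a year: 410/2 = 205.

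At that moment one file is due for review. With even accrual and a constant hazard, about 7 deaths (10% mortality) to 14 deaths (20%) would already have occurred among the 138.

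**4. What file reviews alone could show.** A single look, exact one-sided p ≤ 0.05 against 10%:
- 50 files reviewed (about 188 enrolled): 10 deaths needed. Chance of a signal 56% at 20% mortality and 21% at 15%.
- 100 files reviewed (about 238 enrolled): 16 deaths needed. Chance 87% and 43%.

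**5. A harm check on accruing deaths.** Expected deaths = 0.10 × the sum over patients of the fraction of six-month deaths due by their current follow-up. The trigger is the smallest k with Poisson P(X ≥ k) < 0.05. With even accrual of 300/13 a month and deaths spread uniformly over six months:

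| Month | Expected deaths | Trigger |
|---|---|---|
| 3 | 0.10 × 69.2 × 1.5/6 = 1.7 | 5 |
| 6 | 0.10 × 138.5 × 3/6 = 6.9 | 12 |
| 9 | 0.10 × (69.2 + 138.5 × 3/6) = 13.8 | 21 |
| 12 | 0.10 × (138.5 + 138.5 × 3/6) = 20.8 | 30 |

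**6. Operating characteristics by simulation** (300 patients over 13 months, the four looks above, 10% benchmark). Matched early timing means that deaths and expected deaths both follow an exponential with mean 2 months, confined to six months. That is an assumption, since the documents give no dates of death.

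| True mortality | Chance of a pause, uniform timing | Chance of a pause, matched early timing |
|---|---|---|
| 5% | 0.2% | below 1% |
| 8.7% | about 4% | about 3% |
| 10% | 9% | 8% |
| 15% | 71% | 77% |
| 20% | 99% | 99% |

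If deaths cluster early in this way but expected deaths are computed as if uniform, the chance of a pause at 10% mortality rises to about 41%. Under uniform timing, median enrolment among trials that pause is 199 at 15% mortality and 139 at 20%.

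**The case against.** Four arguments can be made against the point.

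- **Deaths may become known earlier.** A reader might infer that deaths are looked at only at the six-month file review. The documents do not say so. That review serves to settle the diagnosis, quality of life is assessed during follow-up, and study physicians provide active care. This stands. But learning of a death is not the same as having someone assigned to count deaths against a benchmark and act, and no section assigns that.
- **Withholding is limited.** It is initial, depends on the investigator's judgement, and treatment may be started while results are awaited. A reader might turn the plan's 20-40% into 60-120 of 300 patients with tuberculosis left untreated. That figure counts patients who may have tuberculosis, not those whose treatment is withheld. The latter number cannot be derived from the documents.
- **The rule is one choice among several and has modest power.** This also stands. If mortality were 10% instead of the planned 5%, a pause would come only about 8-9% of the time, and at 15% roughly a quarter of trials would never pause. Other schedules or thresholds would be defensible.
- **The benchmark is imperfect.** The plan does not call the 10% a six-month figure, it reflects new cases only, and the study excludes inpatients with suspected tuberculosis while the 2022 figures do not say whether they do. These are reasons to state the benchmark and its sensitivity value, not reasons to have no check.

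**Conclusion.** The point holds as a gap in patient safety: treatment may be withheld initially in a single-arm study, no review of deaths during enrolment or pause rule is described, and the risk section is silent on delayed tuberculosis treatment.

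The figure of about 138 of 300 rests on even accrual and the stated dates; other accrual assumptions give 180 to 205. A reader might take it as the point at which enrolment could first be paused. The documents do not support that. No pause mechanism exists at any point, and a single reviewed file shows nothing about excess mortality. Nor does 138 measure what the proposed check gains: its closeness to the median of 139 at 20% mortality is a coincidence of the month-6 look.

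The operating characteristics depend on the timing used for expected deaths, so the check must be calibrated to the historic group. The 0.05 threshold applies to each look; the chances given above are for all four looks together.

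**What to change.** Add to Methods:

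> All deaths are logged when they become known, with the date and whether tuberculosis treatment was withheld. At 3, 6, 9 and 12 months after first inclusion, cumulative deaths are compared with the number expected from the historic group, given the follow-up accrued and the historic timing of deaths. If the one-sided Poisson probability of at least that many deaths is below 0.05, enrolment pauses for review with the ethics committee.

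Also:
- State the benchmark: 10% as in the sample size calculation, with 8.7% (44/508) as a sensitivity value.
- Take the timing of deaths from the historic group's records, not from an assumed uniform spread. Fix the triggers before the first look.
- State that this is a check for harm only, that it uses no efficacy alpha, and that the absence of a pause is not evidence of safety.
- Reconcile Burden and risks for participants with the withholding described under Intervention. This does not require a rule on how any patient is treated.

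The cost is a protocol amendment, a death log, extraction of death dates for the historic group and four short tabulations. The downside is an unnecessary pause: below 1% at 5% mortality, about 3-4% at 8.7% and about 8-9% at 10% with correct timing, but about 40% at 10% if uniform timing is assumed and deaths cluster early.
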